- Radiologic/objective evidence of recurrence or progression to the most recent systemic therapy for breast cancer
- Radiologic/objective evidence of breast cancer recurrence or progression while on or within 6 months after the end of adjuvant treatment with an AI, or progression while on or within 1 month after the end of prior AI treatment for locally advanced or MBC. The AI (letrozole, anastrozole, or exemestane) does not have to be the most recent treatment before randomization, but patients must have received at least 4 weeks of treatment with an AI.
- Patients must have measurable disease by RECIST v1.1 or non-measurable, evaluable disease with at least one evaluable bone lesion by RECIST v1.1 based on radiologic scans within 28 days of Day 1 of Cycle 1. Bone lesions that have been irradiated are not evaluable.

General Inclusion Criteria

- Signed Informed Consent Form
- Age \geq 18 years
- ECOG Performance Status of 0 or 1 (see [Appendix 8](#))
- Consent to the collection of a formalin-fixed paraffin-embedded (FFPE) block or a minimum of 10 freshly cut unstained tumor slides (submission of 15–20 is strongly encouraged) from archival tumor tissue or a newly collected (“fresh”) tumor sample for protocol-mandated exploratory assessments
- Adequate hematologic and end-organ function, defined by the following laboratory results obtained within 28 days prior to Day 1 of Cycle 1:
 - Absolute neutrophil count \geq 1500/ μ L
 - Platelet count \geq 90,000/ μ L

- Hemoglobin ≥ 9.0 g/dL (90 g/L)
- Albumin ≥ 3.0 g/dL (30 $\mu\text{mol/L}$)
- Total bilirubin $\leq 1.5 \times$ upper limit of normal (ULN)
- Aspartate transaminase (AST), alanine transaminase (ALT), and alkaline phosphatase (ALP) $\leq 1.5 \times$ ULN, with the following exceptions:

Patients with documented liver metastases: AST and/or ALT $\leq 5.0 \times$ ULN

Patients with documented bone metastases: ALP $\leq 5.0 \times$ ULN

Serum creatinine $\leq 1.5 \times$ ULN or creatinine clearance ≥ 50 mL/min based on Cockcroft–Gault glomerular filtration rate (GFR) estimation

$$\frac{(140 - \text{age}) \times (\text{weight in kg}) \times (0.85 \text{ if female})}{72 \times (\text{serum creatinine})}$$

International normalized ratio (INR) < 1.5 and activated partial thromboplastin time (aPTT) $< 1.5 \times$ ULN; for patients requiring therapeutic anticoagulation therapy, a stable INR ≤ 2.5

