4.4 CONCOMITANT THERAPY

4.4.1 Permitted Therapy

Concomitant therapy includes any medication (e.g., prescription drugs, over-the-counter drugs, herbal or homeopathic remedies, nutritional supplements) used by a patient from 7 days prior to screening to the study completion/discontinuation visit. All such medications should be reported to the investigator and recorded on the Concomitant Medications eCRF.

Patients treated with anti-seizure medications should have levels monitored regularly.

Palliative and supportive care for disease-related symptoms may be administered at the investigator's discretion. Patients who experience toxicities should have their symptoms treated as clinically indicated. Anti-emetics and anti-diarrheal medications should not be

administered prophylactically before initial treatment with study drug. At the discretion of the investigator, prophylactic anti-emetic and/or anti-diarrheal medication(s) may be used as per standard clinical practice before subsequent doses of study drug.

Pain medications administered per standard clinical practice are allowed. Bone-sparing agents (e.g., bisphosphonates, denosumab) for palliation of bone metastases or for the treatment of osteoporosis/osteopenia are allowed, but initiation of such agents or modification of the pre-study bisphosphonate or denosumab treatment regimen require the approval of the Medical Monitor and should be avoided where possible.

GDC-0810 was shown to inhibit human CYP2B6 and CYP2C enzymes in vitro; therefore, drug-drug interactions with co-administered CYP2B6 and CYP2C substrates cannot be excluded and should be avoided where possible. Note that many of these medications are also metabolized by other CYP enzymes which are not inhibited by GDC-0810 (e.g., CYP3A4), thus attenuating the potential for drug-drug interactions to some extent. If there is clinical need for a particular CYP2B6 or CYP2C substrate drug, dose adjustments and/or use of alternative medications are recommended.

A list of possible CYP2B6 and CYP2C substrates can be found in [Appendix 9](#).

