4.4.2 Prohibited Therapy

Use of the following concomitant therapies is prohibited for at least 14 days prior to Cycle 1 Day 1 dosing and during the study treatment:

- Therapy intended for the treatment of cancer (regulatory-approved or experimental), including chemotherapy, radiation therapy, immunotherapy, biologic therapy, herbal therapy, radiopharmaceutical therapy, or endocrine therapy.

Local radiotherapy is not permitted. It is understood that there may be extreme circumstances requiring local radiotherapy in which the investigator does not believe that the symptoms are a result of disease progression (e.g., impending fracture), and the radiation field does not encompass a target/non-target lesion. In such cases, the investigator must obtain approval from the Medical Monitor, and such patients should have a tumor assessment of the lesion(s) before they actually receive the radiotherapy. If a patient received radiation therapy and a target or non-target lesion is included in the field of radiation, the lesion(s) will become unevaluable for tumor response.

Further reasons for avoiding local radiotherapy include the difficulty in distinguishing new symptomatic pain or worsening of lytic bone lesions from disease progression. Radiation therapy to a specific site renders that lesion unevaluable for tumor response. Previous clinical experience also suggests that new bone pain is frequently a symptom of disease progression. Bone pain secondary to study treatment can be treated with pain medications, nonsteroidal anti-inflammatory drugs, or corticosteroids.

Use of the following concomitant therapies is prohibited for at least 7 days prior to Cycle 1 Day 1 dosing and during the study treatment:

- Hematopoietic growth factors (e.g., erythropoietins, G-CSF, and GM-CSF) are not to be administered prophylactically. Use of these agents should be reserved for cases of severe neutropenia and anemia per the labeling of these agents and require the approval of the Medical Monitor.
- Hormone replacement therapy, topical estrogens (including any intra-vaginal preparations), megestrol acetate and selective ER modulators (e.g., raloxifene) are prohibited.
- Owing to their narrow therapeutic index and the potential for drug-drug interactions, concomitant therapy with warfarin or phenytoin is prohibited. Please see [Appendix 9](#) for further information.

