5.1.4.2 Venous Thromboembolic Events

An increased risk of VTE is known to be associated with some endocrine therapies such as tamoxifen.

As of a data cutoff of 9 September 2016, safety data from 148 patients treated with GDC-0810 in the Phase Ia, IIa, and non-palbociclib containing Ib components of Study GO29642 were reviewed. Among the 148 patients, 9 experienced at least one adverse event of thromboembolism (defined by MedDRA SMQ narrow of embolic and thrombotic events, venous). Preferred terms were deep vein thrombosis, pulmonary embolism and venous thrombosis. Events ranged from Grade 2 to 4 in severity, and all were treated with anticoagulation.

Patients should be advised to seek immediate medical attention if they become aware of any symptoms of pulmonary embolism or deep vein thrombosis, such as acute onset of chest pain, shortness of breath, or swelling in extremities. Investigators should manage and treat patients suspected to have a VTE according to [Table 1](#).

Thromboembolic events (e.g., pulmonary embolism, deep vein thrombosis) of Grade ≥ 2 , regardless of seriousness or causality, should be reported immediately to the Sponsor (see Section 5.2).

See [Table 1](#) for guidelines on the management of VTEs.

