Grade 1 – 2	
 • Manage and treat patients according to institutional guidelines and local standards of care. • May consider anti-coagulation and/or IVC filter based upon local best standards and practices after an individual assessment of risk benefit for each patient.
Grade ≥ 3	
 • As Grade 1–2. • Hold dosing with GDC-0810 until the patient is stable. • Discuss with study Medical Monitor for appropriate dose modification and management.
Elevation of Hepatic Transaminases:	
General	
 • Patients presenting with jaundice, coagulopathy, abdominal pain, or other symptoms suggestive of hepatic pathology should have their liver function tests checked and imaging of the liver performed. If the liver enzymes are elevated with no obvious malignant cause found, a hepatologist specialist should be consulted. • Patients experiencing hepatic enzyme elevation should be treated and managed per standard of care. Per Section 5.3.5.6, investigators must report the occurrence of abnormal liver function tests meeting Hy's law criteria as an adverse event.
Grade ≥ 3	
 • Hold study drug until resolution to baseline or below ULN.

AESI = adverse event of special interest (see Section 5.2.3); DVT = deep vein thrombosis; GI = gastrointestinal; IVC = inferior vena cava; PE = pulmonary embolism; VTE = venous thromboembolic event; ULN = upper limit of normal.

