- ^l Transvaginal ultrasounds should be performed to monitor endometrial thickness during the study at screening, at the study drug discontinuation visit, and additionally when clinically indicated (e.g., to evaluate vaginal bleeding). *Transvaginal ultrasounds are not required for patients who have had a hysterectomy.*
- ^m Perform tumor assessments at screening *per institutional guidelines* and additionally when clinically indicated for all patients. Screening assessments must include CT scans of the chest, abdomen and pelvis; CT scans of the neck and brain imaging should be included if clinically indicated. A documented standard-of-care tumor assessment performed within 28 days before Cycle 1 Day 1 may be used for the screening assessment, provided it meets the above requirements. The same imaging method used at screening must be used throughout the study. Response assessments will be performed by the investigator, on the basis of physical examinations and imaging scans. Bone disease identified on bone imaging should be evaluated radiographically by CT scan, magnetic resonance imaging (MRI), or X-ray. The same modality used at screening should be used throughout the study.
- ⁿ An isotope bone scan (e.g., technetium) will be performed at screening and should be repeated in the event of clinical suspicion of progression of existing bone lesions and/or the development of new bone lesions or for confirmation of complete response for all patients. For patients with bone-only disease not visible on the CT or MRI scans being performed as part of the tumor assessments, bone scans should be repeated when clinically indicated until disease progression.
- ^o Includes white blood cell (WBC) count with differential (neutrophils, eosinophils, basophils, lymphocytes, and monocytes), red blood cell (RBC) count, hemoglobin, hematocrit, and platelet count. Reporting the differential as absolute counts is preferred, but percent is accepted. Pre-dose laboratory samples may be drawn within 2 days prior to the cycle visit (except Cycle 1 Day 1, which must be drawn at that visit).
- ^p aPTT and INR should be collected at screening and as clinically indicated thereafter. For patients taking warfarin or its equivalent, aPTT and INR should be measured twice in the first week of administration and then as clinically indicated.

Appendix 1

Schedule of Assessments for Patients on Arm A (GDC-0810) (cont.)

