Appendix 9 Substrates and Inhibitors of CYP Enzymes

The following drugs are sensitive substrates or substrates of CYPs 2C8, 2C9 and 2C19 with a low therapeutic window. It is strongly recommended to consider alternate therapies, whenever possible. It is not possible to produce an exhaustive list of medications that fall into these categories, so if in question, refer to the appropriate product label.

CYP Enzymes	Sensitive Substrates	Substrates with Narrow Therapeutic Range
CYP2B6	Bupropion, efavirenz	
CYP2C8	Repaglinide	Paclitaxel
CYP2C9	Celecoxib	Warfarin, phenytoin (neither drug should be used concomitantly with GDC-0810)
CYP2C19	Clobazam, lansoprazole, omeprazole, S-mephenytoin	S-mephenytoin

Source: FDA draft guidance on “Drug Interaction Studies Study Design, Data Analysis, Implications for Dosing, and Labeling Recommendations,” Feb 2012. Can be accessed from: <http://www.fda.gov/downloads/Drugs/GuidanceComplianceRegulatoryInformation/Guidances/ucm292362.pdf>.

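### Section 4.4.2 prohibits warfarin during study treatment, but the coagulation footnotes of both schedules say how to monitor patients taking it, and the ban's scope by arm is unclear

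*Combined protocol and SAP*

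**What the plan says.** **The ban.** Section 4.4.2 states that "concomitant therapy with warfarin or phenytoin is prohibited". It sits in a list of therapies that are "prohibited for at least 7 days prior to Cycle 1 Day 1 dosing and during the study treatment". It has no exception and no limit by arm. Appendix 9 lists warfarin and phenytoin under CYP2C9 and adds that "neither drug should be used concomitantly with GDC-0810".

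**The schedules.** The coagulation row of each schedule runs through the treatment cycles as clinically indicated and refers to a footnote. In Appendix 1 (Arm A, footnote p) that footnote says: "For patients taking warfarin or its equivalent, aPTT and INR should be measured twice in the first week of administration", and then as clinically indicated. The coagulation footnote of Appendix 2 (Arm B) has the same sentence.

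**VTE management.** Section 5.1.4.2 reports the earlier VTE cases, says that "all were treated with anticoagulation", and sends investigators to Table 1. The Grade 1–2 VTE row of Table 1 reads in part: "May consider anti-coagulation and/or IVC filter based upon local best standards and practices". The row for Grade 3 and above refers back to it, holds GDC-0810 until the patient is stable, and asks for discussion with the Medical Monitor. Neither Section 5.1.4.2 nor Table 1 mentions the warfarin ban or Section 4.4.2.

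**Related text.** Section 4.4.1 treats CYP2C substrates in general more softly: "If there is clinical need for a particular CYP2B6 or CYP2C substrate drug, dose adjustments and/or use of alternative medications are recommended". It does not set warfarin apart. Section 5.1.5 advises caution when fulvestrant is given to patients using anticoagulants.

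**The concern.** One part of the protocol forbids a drug throughout treatment, and another tells sites what to do for patients taking it. A site that reads only the schedule could reasonably conclude that warfarin is allowed with INR checks. A site that reads Section 4.4.2 would conclude that it is not allowed.

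The disagreement matters because VTE is listed as a potential risk of GDC-0810 and the VTE guidance leads towards anticoagulation. Enrollment is closed, but patients with clinical benefit may continue on either drug, so the instructions are still in use. The Internal Monitoring Committee no longer follows patient safety. Monitoring has passed to the Sponsor, and sites rely on the written text. Section 9.2 does not allow prospective requests to deviate, so the footnote cannot be treated as an agreed exception to Section 4.4.2.

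**Working it through.** The plan gives no figure to reproduce. The check is a comparison of texts, followed by a short calculation of how likely the situation is.

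**Step 1: the texts side by side**

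| Place | Arm covered | Position on warfarin |
|---|---|---|
| Section 4.4.2 | Not limited | Prohibited from at least 7 days before Cycle 1 Day 1 and during treatment |
| Appendix 9 | GDC-0810 only | Not to be used together |
| Appendix 1, coagulation footnote | Arm A | INR and aPTT monitoring for patients taking it |
| Appendix 2, coagulation footnote | Arm B | Same sentence |
| Section 5.1.4.2 and Table 1, VTE rows | GDC-0810 | Not named; anticoagulation left to local practice; no reference to the ban |

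**Step 2: can the footnote be read so that it fits the ban?** The first week of administration could mean the first week of study drug. The footnote then presupposes a patient who starts study treatment while on warfarin. It could instead mean the first week of warfarin, and the footnote then presupposes warfarin begun during the study. Section 4.4.2 excludes both. The footnote does not mention a prohibition, a deviation or stopping warfarin, so it does not read as a rule for handling violations. It also extends to equivalents of warfarin, a class that neither Section 4.4.2 nor Appendix 9 defines.

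**Step 3: by arm.** In Arm A the footnote conflicts with both Section 4.4.2 and Appendix 9. In Arm B it conflicts with Section 4.4.2 as worded, but not with Appendix 9. The interaction described in Section 4.4.1 is inhibition of CYP enzymes by GDC-0810, and Section 5.1.5 asks only for caution with anticoagulants on fulvestrant. The documents therefore do not settle whether the ban is meant to cover Arm B.

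**Step 4: the route to a breach.** Take a continuing Arm A patient with a Grade 2 VTE. Table 1 permits anticoagulation by local practice and, at that grade, gives no instruction to hold GDC-0810. If local practice is warfarin, the footnote supplies the monitoring. The site has followed Table 1 and Appendix 1 and has breached Section 4.4.2.

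**Step 5: how likely a VTE is**

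- Input from Sections 1.2.2 and 5.1.4.2: 9 of 148 patients in Study GO29642, so p = 9/148 = 0.0608, or 6.1%.
- The number of patients continuing on GDC-0810 is not given. Assumed: n = 5, 10 or 20.
- Formula: P(at least one VTE) = 1 − (1 − p)^n, with patients independent and at the same risk.
- n = 5: 1 − 0.9392^5 = 0.27.
- n = 10: 1 − 0.9392^10 = 0.47.
- n = 20: 1 − 0.9392^20 = 0.71.

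These are chances of a VTE, not of warfarin use. The documents say the earlier cases were anticoagulated but do not name the agent, so no rate of warfarin use can be derived.

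**The case against.** The strongest reply is that Section 4.4.2 is clear and applies throughout treatment whether or not other sections repeat it. On this view the footnote only sets a laboratory check, measuring INR breaches nothing, and a site that reads the whole protocol will not give warfarin. It is true that the footnote does not authorise the drug. It does presuppose patients on treatment who are taking it, and Section 4.4.2 leaves no room for such patients. That part of the concern stands.

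Three stronger readings are tempting, and the documents do not support them.

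- **That eligibility contradicts the ban.** Section 4.1.1 includes the wording "for patients requiring therapeutic anticoagulation therapy, a stable INR" and sets its limit at 2.5. A reader might infer that this admits patients on warfarin. The criterion names no agent. Its laboratory window is 28 days before Cycle 1 Day 1, while the ban starts at least 7 days before, so a patient could meet both. With enrollment closed the criterion no longer operates.
- **That Table 1 contradicts the ban.** It refers to anticoagulation as a class and never mentions warfarin. For Grade 3 and above it also holds GDC-0810 and involves the Medical Monitor. What is missing is a cross-reference; the text itself does not conflict.
- **That the situation is bound to arise.** Half of the planned 152 patients is 76. At 6.1% that gives 76 × 0.0608 = 4.6 VTE patients and a chance of at least one of 1 − 0.9392^76 = 0.99. The arithmetic is right, but the planned arm will not be filled, and the figures count VTE, not warfarin use.

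The 6.1% is itself approximate. It comes from another study, whose Phase Ia part used 100 to 800 mg in patients with a median of 4 prior systemic treatments, and it is not adjusted for time on treatment.

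**Conclusion.** The inconsistency is real and the protocol is wrong as written. It is direct in Arm A. In Arm B it shows that the scope of the ban is undefined. The missing cross-reference in the VTE guidance makes an inadvertent breach possible for a patient who continues on GDC-0810.

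The textual finding depends on no assumption. The statement that the situation may arise rests on carrying the GO29642 rate over to this trial and on the assumed 5 to 20 continuing patients, which gives a chance of at least one VTE between about 27% and 71%. The point concerns safety instructions to sites and does not touch the efficacy analysis. It should be corrected. Which rule on warfarin is clinically right is not judged here.

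**What to change.** 1. Reconcile Section 4.4.2, Appendix 9 and the coagulation footnotes of Appendices 1 and 2 so that all four state the same rule on warfarin.
2. State that rule explicitly for each arm, and say whether it extends to the equivalents that the footnotes mention.
3. Cross-refer to the rule from the VTE rows of Table 1. A matching reference in Section 5.1.4.2, and a line in Section 4.4.1 saying whether its general advice on CYP2C substrates applies to warfarin, would remove the remaining ambiguity.
4. Leave Section 4.1.1 as it is. It does not name warfarin, and no further patients will be screened.

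The content of the rule is for the sponsor to decide on clinical grounds. The cost is wording in an amendment or a letter to sites.

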Appendix 2 Schedule of Assessments for Patients on Arm B (Fulvestrant)

	Screening ^a	Cycle 1		Cycle 2	Cycle 3	Cycle 4	Cycles 5+	Study Drug Discontinuation ^b	
Day (Window)	-28 to -1	1	15 (+1) ^c	1 (+1) ^c	1 (±1) ^c	1 (±3) ^c	1 (±3) ^c	Within 30 days after last dose	
Informed consent ^d	x								
Medical history and demographic data ^e	x								
Concomitant medications ^f	x	x	x	x	x	x	x	x	
Adverse events ^g	x	x	x	x	x	x	x	x	
Vital signs ^h	x	x	x	x	x	x	x	x	
Complete physical examination, height, weight ^j	x								
Limited physical examination ^k		x	x	x	x	x	x	x	
ECOG performance status	x	x	x	x	x	x	x	x	
Single 12-lead ECG	x	As clinically indicated							
Endometrial thickness assessment ^l	x	As clinically indicated							x
Tumor assessment ^m	x	x^{i, n}							x
Bone scan ⁿ	x	Per clinical indication ⁿ							
CBC with differential ^o	x	x	x	x	x	x	xⁱ	x	
Coagulation (INR, aPTT) ^p	x	As clinically indicated (see footnote)							
Blood chemistry ^q	x^q	x	x	x	x	x	xⁱ	x^q	
FSH and estradiol ^r	x^r								
Urinalysis ^s	x	As clinically indicated							
Archival (or fresh) FFPE tumor tissue ^t	x								

Appendix 2
Schedule of Assessments for Patients on Arm B (Fulvestrant) (cont.)

	Screening ^a	Cycle 1		Cycle 2	Cycle 3	Cycle 4	Cycles 5+	Study Drug Discontinuation ^b
Day (Window)	-28 to -1	1	15 (+1) ^c	1 (+1) ^c	1 (±1) ^c	1 (±3) ^c	1 (±3) ^c	Within 30 days after last dose
Plasma sample for ctDNA and plasma biomarkers ^u		x			x		x	x
Plasma sample for potential CDx ^v		x			x			
Optional blood sample for WGS ^w		x						
Optional tumor biopsy at progression ^x								x
Fulvestrant administration ^y		x	x	x	x	x	x	

Appendix 2

Schedule of Assessments for Patients on Arm B (Fulvestrant) (cont.)

aPTT=activated partial thromboplastin time; CBC=complete blood count; CDx=companion diagnostic; CT=computed tomography; ECG=electrocardiogram; ECOG=Eastern Cooperative Oncology Group; eCRF=electronic Case Report Form; EORTC=European Organization for Research and Cancer; FFPE=formalin-fixed, paraffin-embedded; FSH=follicle stimulating hormone; INR=international normalized ratio; PK=pharmacokinetic; PRO=patient-reported outcome; q12=every 12 (weeks); QLQ-BR23=Quality Of Life Questionnaire Breast Cancer Module; QLQ-C30=Quality of Life Questionnaire; TSQM=Treatment Satisfaction Questionnaire for Medication; WGS =whole genome sequencing.

Notes: All assessments should be performed within the indicated window unless otherwise specified. On treatment days, all assessments should be performed prior to dosing, unless otherwise specified. Patients should receive their first dose of study treatment on the day of randomization if possible, but no later than 5 business days after randomization.

- ^a Results of standard-of-care tests or examinations performed prior to obtaining informed consent and within 28 days prior to Day 1 may be used; such tests do not need to be repeated for screening.
- ^b Patients who discontinue study drug for any reason other than death will return to the clinic for a treatment discontinuation visit within 30 days after the last dose of study drug. Patients must be followed for safety assessment for at least 28 days after completion of study drug. The visit at which response assessment shows disease progression may be used as the study drug discontinuation visit provided that all tests required at the study drug discontinuation visit are performed.
- ^c The visit window for Cycle 1 Day 15 and Cycle 2 Day 1 is +1 day since fulvestrant administration should not occur prior to Cycle 1 Day 15 or Cycle 2 Day 1. The visit window for Cycle 3 Day 1 is ± 1 day and the visit window for Day 1 of Cycles 4 and up is ± 3 days. Visits are based on a 28-day cycle. If the timing of a protocol-mandated procedure coincides with a holiday and/or weekend that precludes the procedure within the allotted window, the procedure must be performed on the nearest following date. The date of Cycle 1 Day 1 should be used to calculate all subsequent target visit dates.
- ^d Informed consent must be documented before any study-specific screening procedure is performed.
- ^e Medical history includes clinically significant diseases within the previous 5 years before Cycle 1 Day 1, smoking history and breast cancer history (including tumor characteristics such as hormone receptor status, prior cancer therapies, surgeries, and procedures). Demographic data include age, sex, and self-reported race/ethnicity where allowed by local regulatory authorities.
- ^f Concomitant medications include prescription medication, over-the-counter preparations, and herbal or homeopathic remedies and supplements used within 7 days prior to the screening visit through the study drug discontinuation visit. After the study drug discontinuation visit, only medications administered for ongoing or new treatment-related adverse events or as anti-cancer therapy will be collected.

Appendix 2

Schedule of Assessments for Patients on Arm B (Fulvestrant) (cont.)

- ^g After informed consent has been obtained but prior to initiation of study drug, only serious adverse events caused by a protocol-mandated intervention should be reported. After initiation of study drug, all adverse events will be reported until 28 days after the last dose of study drug. After this period, investigators should report any deaths, serious adverse events, or other adverse events of concern that are believed to be related to prior treatment with study drug. The investigator should follow each adverse event until the event has resolved to baseline grade or better, the event is assessed as stable by the investigator, the patient is lost to follow-up, or the patient withdraws consent. Every effort should be made to follow all serious adverse events considered to be related to study drug or trial-related procedures until a final outcome can be reported. Please note, additional information will be collected if diarrhea is reported as an adverse event.
- ^h Vital signs include measurements of heart rate, systolic and diastolic blood pressures while the patient is in a seated position, and oral or tympanic temperature. Record abnormalities on the Adverse Event eCRF.
- ⁱ *To be performed per institutional guidelines and/or as clinically indicated except physical examination, ECOG, vital signs creatinine liver function tests, adverse events, concomitant medication, and study drug compliance should be monitored at each cycle.*
- ^j Complete physical examination includes evaluation of the head, eyes, ears, nose, and throat, and the cardiovascular, dermatological, musculoskeletal, respiratory, gastrointestinal, genitourinary, and neurological systems. Record abnormalities observed at baseline on the General Medical History and Baseline Conditions eCRF.
- ^k Perform a limited, symptom-directed examination at specified timepoints or as clinically indicated. Record new or worsened clinically significant abnormalities on the Adverse Event eCRF.
- ^l Transvaginal ultrasounds should be performed to monitor endometrial thickness during the study at screening, at the study drug discontinuation visit, and additionally when clinically indicated (e.g., to evaluate vaginal bleeding). *Transvaginal ultrasounds are not required for patients who have had a hysterectomy.*
- ^m Perform tumor assessments at screening *per institutional guidelines* and additionally when clinically indicated for all patients. Screening assessments must include CT scans of the chest, abdomen and pelvis; CT scans of the neck and brain imaging should be included if clinically indicated. A documented standard-of-care tumor assessment performed within 28 days before Cycle 1 Day 1 may be used for the screening assessment, provided it meets the above requirements. The same imaging method used at screening must be used throughout the study. Response assessments will be performed by the investigator, on the basis of physical examinations and imaging scans. Bone disease identified on bone imaging should be evaluated radiographically by CT scan, MRI, or X-ray. The same modality used at screening should be used throughout the study.
- ⁿ An isotope bone scan (e.g., technetium) will be performed at screening and should be repeated in the event of clinical suspicion of progression of existing bone lesions and/or the development of new bone lesions or for confirmation of complete response for all patients. For patients with bone-only disease not visible on the CT or MRI scans being performed as part of the tumor assessments, bone scans should be when clinically indicated until disease progression.

Appendix 2

Schedule of Assessments for Patients on Arm B (Fulvestrant) (cont.)

- ° Includes white blood cell (WBC) count with differential (neutrophils, eosinophils, basophils, lymphocytes, and monocytes), red blood cell (RBC) count, hemoglobin, hematocrit, and platelet count. Reporting the differential as absolute counts is preferred, but percent is accepted. Pre-dose laboratory samples may be drawn within 2 days prior to the cycle visit (except Cycle 1 Day 1, which must be drawn at that visit).
- ° aPTT and INR should be collected at screening and as clinically indicated thereafter. For patients taking warfarin or its equivalent, aPTT and INR should be measured twice in the first week of administration and then as clinically indicated.
- ° Blood chemistry includes the following: glucose, blood urea nitrogen or urea, creatinine, sodium, potassium, chloride, magnesium, bicarbonate, calcium, total protein, albumin, total bilirubin, alkaline phosphatase, AST and ALT. Samples for blood chemistry should be drawn predose, and may be drawn within 2 days prior to the cycle visit (except Cycle 1 Day 1, which must be drawn at that visit). Screening blood chemistry should be drawn after fasting (≥ 8 hours) at treatment and at the study drug discontinuation visit, but may be drawn nonfasting at all other timepoints.
- ° FSH and estradiol to be collected only when required to assess study eligibility (see Section 4.1.1).
- ° Urinalysis includes dipstick macro (specific gravity, pH, glucose, protein, ketones and blood). A reflex microscopic urinalysis (RBCs, WBCs, casts, etc.) should be performed if the macroscopic analysis is abnormal.
- ° Archival tumor tissue blocks or a minimum of 10 (15–20 preferred) freshly cut unstained slides from the most recent tumor tissue will be collected at screening for molecular characterization of the tumor tissue, including but not limited to *ESR1* mutations.
- ° A plasma sample will be collected for ctDNA and plasma biomarkers, including but not limited to *ESR1* mutations, *PIK3CA* mutations, and *AKT1* mutations on Day 1 of Cycle 1, Cycle 3, Cycle 5, Cycle 7, Cycle 9, and every 3 cycles thereafter, timed to coincide roughly with response assessments. On Cycle 1 Day 1, the sample should be collected prior to study drug treatment.
- ° A plasma sample will be collected and banked for potential future blood-based companion diagnostic development. On Cycle 1, Day 1, sample should be collected prior to study drug treatment.
- ° Collection of a blood sample for whole genome sequencing (see Section 4.5.10) is not required for study participation but is strongly encouraged and will be collected from patients who sign the Optional Research portion of the Informed Consent Form. A blood sample will be collected as a source of normal DNA to determine whether sequence variants detected in tumor tissue are somatic mutations or single nucleotide polymorphisms. A portion of this sample will be used for WGS (see Section 4.5.10). Not applicable for a site that has not been granted regulatory approval for WGS sampling.
- ° Tumor biopsy collection at the time of disease progression is not required for study participation but is strongly encouraged and will be collected from patients who sign the Optional Research portion of the Informed Consent Form.
- ° Fulvestrant will be administered in the clinic as two intramuscular injections of 250 mg each (total dose 500 mg) on Days 1 and 15 of Cycle 1 and Day 1 of each subsequent 28-day cycle.

Appendix 3

Schedule of Pharmacokinetic Assessments (for Arm A only)

Study Visit	Timepoint	Assessment
Cycle 1, Day 1	Predose	GDC-0810 PK
	3 hours postdose	GDC-0810 PK
Cycle 3, Day 1 (± 1 day)	Predose	GDC-0810 PK
	3 hours postdose	GDC-0810 PK

Notes: Predose samples should be collected within 30 minutes before administration of GDC-0810. All other sample draw times are ±5 minutes. The plasma sample will be split into two equal aliquots: a primary sample and a back-up sample.

Detailed instructions for PK plasma sample preparation and shipping will be provided to the study sites in a separate Laboratory Manual.

Record exact date and time of all study drug doses and PK sample collections.

Appendix 7

Response Evaluation Criteria in Solid Tumors, V 1.1

Modified Excerpt from Original Publication

Selected sections from the Response Evaluation Criteria in Solid Tumors (RECIST), Version 1.1,¹ are presented below, with slight modifications and the addition of explanatory text as needed for clarity.²

MEASURABILITY OF TUMOR AT BASELINE

DEFINITIONS

At baseline, tumor lesions and/or lymph nodes will be categorized as measurable or non-measurable as described below.

MEASURABLE TUMOR LESIONS

Tumor Lesions. Tumor lesions must be accurately measured in at least one dimension (longest diameter in the plane of measurement is to be recorded) with a minimum size as follows:

- 10 mm by computed tomography (CT) or magnetic resonance imaging (MRI) scan (CT/MRI scan slice thickness/interval no greater than 5 mm)
- 10-mm caliper measurement by clinical examination (lesions that cannot be accurately measured with calipers should be recorded as non-measurable)
- 20 mm by chest X-ray

Malignant Lymph Nodes. To be considered pathologically enlarged and measurable, a lymph node must be ≥ 15 mm in the short axis when assessed by CT scan (CT scan slice thickness recommended to be no greater than 5 mm). At baseline and at follow-up, only the short axis will be measured and followed. See also notes below on “Baseline Documentation of Target and Non-Target Lesions” for information on lymph node measurement.

¹ Eisenhauer EA, Therasse P, Bogaerts J, et al. New response evaluation criteria in solid tumors: revised RECIST guideline (Version 1.1). *Eur J Cancer* 2009;45:228–47.

² For consistency within this document, the section numbers and cross-references to other sections within the article have been deleted and minor formatting changes have been made.

Appendix 7

Response Evaluation Criteria in Solid Tumors, V 1.1

Modified Excerpt from Original Publication (cont.)

NON-MEASURABLE TUMOR LESIONS

Non-measurable tumor lesions encompass small lesions (longest diameter < 10 mm or pathological lymph nodes with short axis ≥ 10 but < 15 mm) as well as truly non-measurable lesions. Lesions considered truly non-measurable include leptomeningeal disease, ascites, pleural or pericardial effusion, inflammatory breast disease, lymphangitic involvement of skin or lung, peritoneal spread, and abdominal mass/abdominal organomegaly identified by physical examination that is not measurable by reproducible imaging techniques.

SPECIAL CONSIDERATIONS REGARDING LESION MEASURABILITY

Bone lesions, cystic lesions, and lesions previously treated with local therapy require particular comment, as outlined below.

Bone Lesions:

- Bone scan, positron emission tomography (PET) scan, or plain films are not considered adequate imaging techniques for measuring bone lesions. However, these techniques can be used to confirm the presence or disappearance of bone lesions.
- Lytic bone lesions or mixed lytic–blastic lesions, with identifiable soft tissue components, that can be evaluated by cross-sectional imaging techniques such as CT or MRI can be considered as measurable lesions if the soft tissue component meets the definition of measurability described above.
- Blastic bone lesions are non-measurable.

Cystic Lesions:

- Lesions that meet the criteria for radiographically defined simple cysts should not be considered as malignant lesions (neither measurable nor non-measurable) since they are, by definition, simple cysts.
